Protocol

Alcohol Metabolism and Disease Risk in Asians

NCT number NCT04967599

Document Date 08/08/2024

Protocol

This exploratory/developmental pilot study uses a parallel study design with a brief online behavioral intervention component. Participants are 360 college students of Asian heritage recruited as two cohorts, a group of incoming first year college students and a group of college students already on campus who report having flushed when they first started drinking alcohol. After a baseline assessment including surveys and DNA collection for genotyping, participants are randomized in equal numbers into one of three feedback groups (n = 120 per group) based on lifetime drinking (Incoming cohort only) and having an ALDH2*2 allele: 1) Phenotype only (PHEN): this intervention provides information on health-related risk associated with alcohol consumption and alcohol metabolism gene variations plus personalized feedback on flushing phenotype and associated risks; 2) Phenotype and Genotype (PHEN+GENE): the PHEN intervention plus personalized feedback on alcohol metabolism genotypes and associated health-related risks; or 3) CONTROL: an attention control session that does not provide feedback included in PHEN or GENE. Participants then are followed in four post-intervention behavioral surveys over 10 months and in the final 10-month follow-up also complete an evaluation of the study and retention of the intervention information. Our alcohol outcome measures include peak quantity (primary) and secondary measures of drinking frequency, weekend drinking, and total amount of drinking. Additional secondary outcome behaviors include percent of time used flush cures when drinking and transition to drinking in initial non-drinkers.

Data Analysis Plan

Alcohol Metabolism and Disease Risk in Asians

NCT number NCT04967599

Document Date 08/08/2024

Data Analysis Plan

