We conduct nonparametric group comparisons to test for group differences among the three intervention groups in our primary and secondary outcomes. For outcomes that are continuous (alcohol consumption measures), we conduct the Kruskal-Wallis test. For the non-drinker and the flush cure use outcomes that are categorical, we conduct either the uncorrected chi-squared test when all of the expected cell counts are at least 5, or the Fisher's exact test when any of the expected cell count is less than 5. We adjust the p-value for significance to a more conservative value of <.01 to adjust for multiple comparisons.

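### Should the flat p < .01 have been a Holm step-down at .05 for the five secondary outcomes?

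*Combined protocol and SAP*

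**What the plan says.** The Protocol section opens by stating the study's standing: "This exploratory/developmental pilot study uses a parallel study design". Participants are "randomized in equal numbers into one of three feedback groups (n = 120 per group", 360 in all. The outcomes are ranked: "Our alcohol outcome measures include peak quantity (primary) and secondary measures of drinking frequency, weekend drinking, and total amount of drinking". Two more follow: "Additional secondary outcome behaviors include percent of time used flush cures when drinking and transition to drinking in initial non-drinkers". That makes one primary and five secondaries. On follow-up it says: "Participants then are followed in four post-intervention behavioral surveys over 10 months".

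The Data Analysis Plan runs three-group tests "to test for group differences among the three intervention groups in our primary and secondary outcomes": Kruskal-Wallis for the consumption measures, and chi-squared or Fisher's exact "For the non-drinker and the flush cure use outcomes that are categorical". One sentence then sets the significance rule for all of them: "We adjust the p-value for significance to a more conservative value of <.01 to adjust for multiple comparisons". The plan gives no overall error level, no count of comparisons, no step-down or gate, and no statement of which survey is tested.

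**The concern.** Three features catch the eye.

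- There are five secondaries, and .05/5 is exactly .01, so the cut-off reads as a Bonferroni limit for that family.
- Holm is never less powerful than Bonferroni at the same familywise level. A Bonferroni limit without the step-down therefore looks like power lost for nothing.
- The Protocol ranks its outcomes, but the significance rule treats the primary and the secondaries alike.

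If the criticism were right, some real secondary effects would be reported as non-significant although a rule with the same 5% limit would have accepted them. A change of wording, made before outcome data are examined, would recover them.

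**Working it through.** **Inputs.** From the documents: one primary, five secondaries, cut-off .01, four post-intervention surveys, three groups. Assumed, because the documents are silent: an overall level of .05, and all effect sizes.

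**1. Can .01 be derived?** Bonferroni for five gives .05/5 = .0100, and for six .05/6 = .0083. Šidák gives 1 − .95^(1/5) = .0102 and 1 − .95^(1/6) = .0085. Only .05/5 matches exactly. That requires leaving the primary out, whereas the plan's sentence covers primary and secondary outcomes together. The match may be coincidence; .01 is also a conventional strict level.

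**2. Does the flat rule control error with one test per outcome?**

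| Outcomes | Bound | If independent |
|---|---|---|
| Five secondaries | 5 × .01 = .05 | 1 − .99^5 = .049 |
| All six | 6 × .01 = .06 | 1 − .99^6 = .059 |

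No inflation arises for the secondaries, and the bound over all six outcomes is 6%.

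**3. Holm over the five secondaries.** The ordered p-values are compared with .05/5, .05/4, .05/3, .05/2, .05/1 = .0100, .0125, .0167, .0250, .0500. If k of them lie below .01, each of the k smallest passes its step, so none is lost. For example, p = .004, .012, .016, .024, .045 gives one finding under the flat rule and five under Holm. The theorem is correct for this family.

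**4. Holm over all six outcomes.** This is the set the plan names. The steps are .0083, .0100, .0125, .0167, .0250, .0500. If the smallest p-value is .009, the flat rule accepts it and Holm stops at once with no finding. In 400,000 simulated sets of six p-values, skewed toward small values, Holm added 18,318 findings and lost 9,900. It no longer dominates.

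**5. More than one test per outcome.** With four surveys there are 5 × 4 = 20 secondary tests. At .01 the chance of any false secondary claim is 1 − .99^20 = .182 if independent, and about .08 at correlations of .8. Bonferroni would need .05/20 = .0025, so .01 would be too lenient. The criticism would then reverse direction.

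**6. Size of the gain where step 3 applies.** Five 2-df tests, each real effect with an assumed 80% power at .05 (59% at .01), correlation 0 to .7:

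| Real secondaries | Flat .01 | Holm | Gain (points) |
|---|---|---|---|
| 5 | 59% | 68–71% | 9–11 |
| 4 | 59% | 65–66% | 6–7 |
| 3 | 59% | 63% | about 4 |
| 2 | 59% | 61% | about 2 |
| 1 | 59% | 59% | none |

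With 30% power each, five real effects go from 13% to 14–16%.

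**7. What the gain costs.** When some effects are real, Holm's later steps also admit more false claims. With three of five real at 80% power, the chance of a false secondary claim goes from 2.0% to 3.5% (independent). With four of five real it goes from 1.0% to 2.7% (independent) or about 3.4% (correlation .7). All stay within 5%, but each exceeds what the plan now allows.

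**The case for a change.** The strongest case for the criticism is that, for five secondaries tested once each at an overall .05, Holm's advantage is a theorem and not a matter of taste. The change would cost only wording. Leaving peak quantity at .01 would keep the six-outcome bound at 6%. Three of the secondaries measure drinking and respond to the same intervention, so several real effects together are plausible, and that is where Holm gains most.

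The theorem stands. Three things weaken its use here.

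- **Its conditions are not in the plan.** A rule can be called inefficient only against a stated target, and the plan sets no 5% familywise target and no secondary-only family.
- **The change does not settle the complaint about ranking.** With the primary held at .01, a secondary could be accepted at up to .05, so the lead outcome could face the stricter test. Gating the secondaries on the primary would use the ranking. But with five real secondaries at 80% power and a primary at 50% power, average secondary power becomes 35–45%, against 59% under the flat rule.
- **It is not free.** False secondary claims rise as shown, and significance claims at individual surveys would have to be given up.

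One observation survives: the plan does not say which survey, or how many tests per outcome, the cut-off covers. That is a missing detail about the number of tests. It does not show that a flat cut-off was the wrong choice, and until it is known nobody can say whether .01 is strict or lenient for the secondaries.

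**Conclusion.** The concern does not hold. With one test per outcome, the flat .01 bounds the chance of a false claim at 5% over the secondaries and 6% over all six outcomes. The plan calls the cut-off conservative, and the study describes itself as exploratory. Preferring Holm is a choice between valid rules, not the correction of an error.

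The possible gain, 9 to 11 points at best and none when only one secondary is real at the assumed 80% power, depends on three unstated conditions: an overall .05, a family of five, and a single test each. Widen the family to six and Holm can lose findings. Test at four surveys and the power argument no longer applies. All power figures rest on assumed effect sizes, since the documents give none.
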